## 14.1.2Sensitivity Analyses of the ARR

For the NB model the Least Squares means estimates of the ARR at Month 24 and associated CI will be reported for patients having respectively  $\leq 1$  relapse or >1 relapse in the previous 2 years, or since MS diagnosis if diagnosis <24 months. These quantities will be obtained using the LSMEANS statement with the ILINK option.

For the Zero Inflated NB model, the following approach will be used to report the estimates of the ARR at Month 24 and associated CIs for patients having respectively  $\leq 1$  relapse or >1 relapse in the previous 2 years, or since MS diagnosis if diagnosis <24 months. The STORE statement in PROC GENMOD will be used to save the fitted model. Then the fitted model will be used in proc PLM with the SCORE statement and the ILINK and NOOFFSET option.

Standardized deviance residuals will be plotted against the linear predictor to assess the goodness of fit of the model (NB or Zero inflated NB). The STDRESDEV statement with the XBETA option in the GENMOD procedure will be used.

## 14.1.3 Secondary Analyses of the ARR

The secondary analysis of the primary endpoint (ARR at Month 24) will be conducted on the PP population using the same method of the primary analysis.

## 14.1.4 Subgroup Analyses of ARR

The subgroup analyses of the primary endpoint (at Month 24 for the ARR during the follow-up period) will be conducted on the FAS population.

A subgroup analysis at Month 24 of the ARR during the follow-up period for patients completing the study and patients who drop out will be performed. Estimates and CIs for the 2 subgroups will be reported using the same method of the primary analysis.

The same analysis will be performed for patients completing the treatment and patients who do not complete the treatment (i.e., completing Year 1 treatment but not Year 2 treatment) when the number of patients in the last group is greater than 10.

A subgroup analysis at Month 24 of the ARR during the follow-up period will be performed with reference to the type of MS at screening (RRMS, aSPMS, PPMS and CIS).

For the primary outcome, the patterns of missingness will be explored. When the number of missing values is substantial (>5%), multiple imputation methodology will be considered for the analysis of the primary objective. At least 20 imputed datasets will be considered. The ARR at Month 24 for a patient will be considered missing if for that patient the number of relapses at Month 24 is missing or if the Time on Study for that patient is missing. At least the following variables will be considered in the imputation model:

- ARR at Month 24
- Type of MS at screening
- Number of relapses in the previous 2 years
- Age
- Sex
- Baseline Body Mass Index (BMI)
- Compliance

Since we have both continuous and categorical variables in the imputation model the Fully Conditional Specification method will be considered for the imputation. Predictive mean matching will be used for the imputation of the following variables: ARR at Month 24, number of relapses in the previous 2 years, age, baseline BMI and compliance. SAS code for the analysis is available in the appendices.

CCI

Cladribine CLICK-MS MS700568\_0078 Version 7.0

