| | • Baseline scores and change in scores from baseline to Month 6, 12 and 24 for the following PROs (collected via electronic PRO [ePRO] at the practice or at the patient's home): |
| | 14-Item Treatment Satisfaction Questionnaire for Medication (TSQM) |
| | 36-Item Short Form Health Survey (SF-36) |
| | Modified Fatigue Impact Scale – 5-item version (MFIS-5) |
| | Beck-Depression Inventory – Fast Screen (BDI-FS) [7 items] |
| | Work Productivity Activity Impairment – MS (WPAI-MS) [6 items] |
| | • PDDS scale |
| | • Treatment adherence questions, based on modified versions of the Multiple Sclerosis Treatment Adherence Questionnaire (MS-TAQ); data to be collected via ePRO at baseline (modified for self-injectables to assess adherence during last previous injectable DMD treatment) and at the end of Months 1, 2, 13, and 14 (modified for cladribine tablets) |
| | • Proportion of patients experiencing a relapse |
| | • Proportion of patients with relapse associated with hospitalization |
| | • Proportion of patients with relapse associated with glucocorticoid use |
| | • Assessment of previous treatment for MS |
| | Previous DMD(s) received for MS prior to study enrollment, since MS diagnosis |

| | • Passans for discontinuation of provious DMD(s) |
|--------------|---|
| | Reasons for discontinuation of previous DMD(s) |
| | Proportion of patients who discontinue cladribine tablets |
| | • Reason for discontinuation of cladribine tablets |
| | • Elapsed time to discontinuation after first dose |
| | • Number of doses and % of planned doses (as per USPI) received |
| | Subsequent treatment chosen following discontinuation of cladribine tablets |
| | • Assessment of concomitant MS medications used during study period |
| | • The ARR based on the last 24 months (or since MS diagnosis, if diagnosis <24 months) prior to the start of treatment with cladribine tablets (retrospective data) |
| | Safety Outcomes: |
| | • All SAEs, ADRs, AESIs and special situations over a 24-month period |
| | • Absolute lymphocyte count (ALC) assessed as per USPI |
| | • Complete blood count (CBC) and lymphocyte subset information as assessed per routine clinical practice |
| Variables | • Baseline characteristics of patients initiating cladribine tablets: age, sex, weight, race/ethnicity, elapsed time since diagnosis of MS, elapsed time since first symptoms of MS |
| | • Medical history (including prior medications for MS) |
| | Physical and neurological examinations |

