9.3 Variables

The following variables will be collected:

Screening and/or Baseline Visit

- Patient demographics, including: age, sex, weight, self-reported race/ethnicity
- Date of diagnosis of MS, date of first symptoms of MS
- DMD treatments received prior to study enrollment, since MS diagnosis (including medication doses and routes of administration, start dates, stop dates, and reasons for discontinuation)
- Relapse of MS in the 2 years prior to the study period or since MS diagnosis, if diagnosis <24 months (including dates of onset and resolution of relapse)
- Most recent MRI results prior to starting cladribine tablets (baseline MRI), which is expected to have been taken within the prior 90 days (number of T1 Gd+ lesions; number of new T2 lesions compared to most recent prior MRI; number of newly enlarging T2 lesions compared to most recent prior MRI; number of CU lesions; presence of brain atrophy and segmental atrophy)
- Results of MRI in the 2 years prior to study enrollment or since MS diagnosis, if diagnosis <24 months (including prior documentation of number of T1 Gd+ lesions; new or newly enlarging T2 lesions; number of CU lesions; presence of brain atrophy and segmental atrophy)
- Results of neurological examination as per standard of care (e.g., Kurtzke Functional System Scores (FSS), ambulation up to 500 meters and Expanded Disability Status Score [EDSS])
- Results of physical examination as per standard of care
- Hematology assessment (white blood cell count, hemoglobin, hematocrit, platelet count, ALC). If the investigator assesses JCV status, these data should be recorded as well
- Pregnancy, human immunodeficiency virus (HIV), hepatitis B, hepatitis C and tuberculosis test results
- ePRO assessments (treatment adherence questions based on modified versions of the MS-TAQ, TSQM, SF-36, MFIS-5, BDI-FS, WPAI-MS, PDDS)
- Comorbid conditions
- List of all MS symptomatic specific medications taken in the 2 years prior to study enrollment (or since MS diagnosis, if diagnosis <24 months), including medication start and stop dates and reasons for discontinuation

Follow-Up Visits

The anticipated timing of assessments is presented in Table 1: Schedule of Assessments.

- Medication log of cladribine tablets treatment during the study period, including medication start dates, medication stop dates, medication dose (mg), number of dose and reasons for discontinuation

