ARR: Annualized Relapsed Rate; FAS: Full Analysis Set; GENMOD: Generalized Linear Model PP: Per Protocol; SAS: Statistical Analysis System.

\* The sensitivity analysis with the zero inflated binomial model will be considered only if the number of patients without relapses is greater than 5%.

The primary endpoint is derived from the number of relapses collected through the eCRF forms "MS Relapse Report" and "MS Relapse Report Details". A patient will have 0 relapses (at Visit 3 and /or Visit 6) if replied "No" to the leading question "Has patient experienced a new MS relapse since last scheduled or unscheduled visit? (Yes, No)". For patient replying 'Yes', the number of relapses will be derived from the records in the "MS Relapse Report Details" form. If at Visit 3 the answer to the leading question is not collected, then the number of relapses in the first year and the total number of relapses during the second year will be missing. If at Visit 6 the answer to the leading question is not collected, then the number of relapses during the second year will be missing.

For ongoing patients during the study, the Time on Study will take into account the last available date of a patient. This will be used in the interim analyses for all ARR evaluations (primary objective, sensitivity analyses and secondary analyses).

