#### 15.4 Vital Signs

Weight will be collected at Baseline when available. It will be summarized descriptively.

Unit Conversion:

Weight (Kg) =  $0.4536^*$  Weight (lb)

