#### SAS code for multiple imputation analysis (example)

The following SAS code is a reduced example that can be adapted for the analysis:

```
* aval is the ARR at month 24 ;
proc mi data=RELAPDATA out=ARRmiout nimpute=20 seed=123;
    class sex;
    fcs regpmm(blweight aval age);
    var age aval blweight sex;
run;
proc means data= ARRmiout N MEAN STD STDERR MIN MAX;
    by _Imputation_;
    var aval;
    output out=ARRmeans_imputed N=n MEAN=mean STD=std STDERR=stderr
MIN=min MAX=max;
run;
proc mianalyze data= ARRmeans_imputed;
    modeleffects mean;
    stderr stderr;
```

run;

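### The imputation model for the primary ARR names BMI although no height is listed, and omits the observed Year 1 relapse count when only the Visit 6 answer is missing

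*SAP*

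**What the plan says.** **When imputation is used.** SAP 14.1.4 (and Protocol 9.7.2) will consider multiple imputation for the primary objective if more than 5% of values are missing. A patient's Month 24 ARR counts as missing if either the Month 24 relapse number or Time on Study is missing.

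**Imputation variables.** The list is a minimum: "At least the following variables will be considered in the imputation model". It holds the Month 24 ARR, type of MS, number of relapses in the previous 2 years, age, sex, "Baseline Body Mass Index (BMI" and compliance. BMI appears again among the variables for predictive mean matching: "age, baseline BMI and compliance". The example code in the SAP appendix instead has "fcs regpmm(blweight aval age", that is, baseline weight.

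**Body measurements collected.** Protocol 9.3 gives "Patient demographics, including: age, sex, weight, self-reported race/ethnicity". The protocol abstract gives "Baseline characteristics of patients initiating cladribine tablets: age, sex, weight, race/ethnicity". SAP 15.4 says "Weight will be collected at Baseline when available" and adds a pound-to-kilogram conversion. Protocol 11.5 and SAP 11.1 also mention weight only.

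**Relapse counts.** Protocol 9.1.1 collects on-study counts at Months 12 and 24. SAP 14.1.1 sets the missing-data rule by visit. If the Visit 3 answer is absent, the counts for both years are missing. The rule beginning "If at Visit 6 the answer to the leading question is not collected" makes only the second-year count missing. The table in the same section analyses early discontinuers on their observed follow-up and observed relapses.

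**The concern.** There are two separate faults in the one imputation method named for the primary endpoint.

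First, the text asks for a variable that neither document shows how to obtain, while the code uses a different one. A programmer following the text and one following the code would build different models.

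Second, the Year 1 count is a component of the 24-month count. For a patient with Visit 3 answered and Visit 6 unanswered it is known, yet it is neither kept as part of the outcome nor used as a predictor. The only relapse predictor listed is the pre-study count, and the example code has not even that. Known events are set aside, and the imputed ARR may contradict them. If patients who relapsed in Year 1 are also more likely to lack a Visit 6 answer, the mean ARR will be too low.

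**Working it through.** **1. BMI.** The plan has no figure to reproduce here; the check is a comparison of sections. The protocol abstract, Protocol 9.3, Protocol 11.5, SAP 11.1 and SAP 15.4 all list weight, and none lists height. The SAP has BMI in its abbreviation list and in 14.1.4, with no formula. The appendix code uses weight. So text and code disagree, and the source of BMI is undocumented.

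**2. Lower bound on the imputed value.** By SAP 14.1.1, ARR = relapses / days on study × 365.25, which is relapses divided by years on study T. With y₁ relapses observed in Year 1, the ARR cannot be below y₁/T. For y₁ = 2:

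- T = 2 years: 2/2 = 1.0
- T = 2.5 years (Year 2 treatment delayed, SAP Section 5): 2/2.5 = 0.8

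Nothing in the listed model enforces this bound.

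**3. How much the Year 1 count predicts.** The rate m and dispersion k are assumptions; the documents give neither. Under a stationary gamma-Poisson model, the share of variance of the 24-month count explained by the Year 1 count is

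R² = (v + c)² / (v × s), with v = m + km², c = km², s = 2m + 4km².

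For m = 0.2 and k = 1: v = 0.24, c = 0.04, s = 0.56, so R² = 0.28² / (0.24 × 0.56) = 0.583. Over m = 0.1 to 0.4 and k = 0 to 3, R² runs from 0.50 to 0.77.

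**4. Effect on the mean ARR.** Assumptions: m = 0.2, k = 1, 24 months on study for all, Year 1 count observed for all, no other informative predictor in the model, and Visit 6 missing with probability p₀ after no Year 1 relapse and p₁ after at least one.

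- P(no Year 1 relapse) = 1/(1 + m) = 0.8333
- Mean ARR in that group = [m/(1 + m)]/2 = 0.0833
- Mean ARR with a Year 1 relapse = (0.2 − 0.8333 × 0.0833)/0.1667 = 0.7833

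Without the Year 1 count, the estimate tends to the mean of patients with Visit 6 answered:

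[0.8333(1 − p₀) × 0.0833 + 0.1667(1 − p₁) × 0.7833] / [0.8333(1 − p₀) + 0.1667(1 − p₁)]

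| p₀ / p₁ | Overall missing | Without Year 1 count | Relative bias |
|---|---|---|---|
| 10% / 10% | 10.0% | 0.200 | 0% |
| 10% / 30% | 13.3% | 0.1539/0.8667 = 0.178 | −11% |
| 10% / 50% | 16.7% | 0.1278/0.8333 = 0.153 | −23% |

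A simulation of 2 million patients per scenario, at rates 0.1, 0.2 and 0.4 with k = 1, agrees. The bias was −11.0% to −11.2% in the second pattern and −23.1% to −23.4% in the third. Conditioning on the Year 1 count recovered the true mean in all nine scenarios, as it should when missingness depends only on that count.

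**The case against.** **The lists are open and the method is conditional.** Multiple imputation is only to be considered, the variable list is a minimum, and the code is labelled a reduced example to be adapted. This stands: an analyst may add the Year 1 count and use weight. But nothing in the SAP directs either step, and the minimum list still names BMI.

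**Height may be on the case report form.** A reader might infer that height is never collected, so that BMI is missing for every patient and the model cannot run. The documents do not support that. The case report form is not among them, and Protocol 9.3 introduces demographics with the word including. That list is evidently incomplete, since it omits type of MS, which the SAP uses. Physical examination results are also collected with unspecified content. What can be said is that height is not listed and no derivation is given.

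**Few patients may be affected.** SAP 14.1.1 gives early discontinuers an ARR from observed data, and a footnote to Protocol Table 1 has relapse counts recorded on an ongoing basis. Both could shrink the imputed group. However, 14.1.4 makes no exception for early discontinuers, so the share imputed cannot be read from the plan.

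**Imputed zeros.** A reader might infer that a patient with 2 Year 1 relapses will most often be imputed as relapse-free. At an assumed ARR of 0.2, the 24-month zero share is e^(−0.4) = 67% (Poisson) or 1/(1 + 0.4) = 71% (negative binomial, dispersion 1). Those are shares over all patients. Predictive mean matching draws from donors with similar predicted values, so they are not this patient's draw probabilities. An impossible value is possible; its frequency is unknown.

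**Conclusion.** The point holds in a limited form. SAP 14.1.4 names a BMI variable with no documented source and disagrees with its own code, which is a specification fault with an obvious substitute. For patients with Visit 3 answered and Visit 6 unanswered, it imputes the whole Month 24 ARR without the Year 1 count, so the result can contradict relapses already recorded. The bound is y₁/T, so a fixed floor of 1.0 for 2 Year 1 relapses would be wrong for anyone followed beyond 24 months.

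A reader might also infer that the primary estimate is biased. The documents do not show that. The bias figures depend wholly on assumed differences in missingness and on the other predictors being uninformative; equal missingness gives no bias in the mean. What stands without those assumptions is that information already in the database is discarded, and that using it would protect against such bias.

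**What to change.** In SAP 14.1.4 and the appendix code:

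1. Replace BMI with baseline weight, or state where height comes from and how BMI is derived. Make text and code use the same variables.
2. Where Visit 3 is answered and Visit 6 is not, impute the Year 2 count conditional on the Year 1 count and follow-up time, with the listed covariates. Add it to the observed Year 1 count and divide by time on study.
3. Where the Visit 3 answer is also missing, impute the counts for both years.
4. State how a missing Time on Study is handled, since it too makes the ARR missing.
5. Reconcile the missingness rule with SAP 14.1.1: say whether an early discontinuer without a Visit 6 answer is analysed on observed follow-up and relapses or is imputed, and count the 5% trigger accordingly.

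The cost is a short SAP revision and a few lines of code. No new data are needed unless BMI is kept and height proves not to have been recorded.

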## 15 Safety Analyses

Safety analyses will be done on the safety analysis populations, i.e. SAF for the first 24-month period.

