9.7 Data Analysis

Further details will be provided in a Statistical Analysis Plan.

There will be a baseline analysis and 3 interim analyses: The baseline analysis will summarize baseline characteristics. In the first interim analysis, mainly for safety purposes, safety, adherence and PRO data will be analyzed for the subset of the first 30 patients enrolled into the study at the 6-month time point. A second interim analysis on the safety, adherence and PRO data will be performed as soon as 6-month data are available for all patients. The third and full interim analysis will be performed on the 12-month data. The final analysis evaluating the primary and secondary objectives will be on the 24-month data at the end of the study.

All patients enrolled in the study who receive at least 1 dose of cladribine tablets will be included in the analyses. The primary endpoint will be analyzed at Month 24. All secondary endpoints on relapse rates, PROs, MRI, and treatment patterns will be analyzed at Month 12 (12-month interim analysis) and Month 24 (final analysis). PRO data will additionally be analyzed once the first 30 patients reach the 6-month follow-up as well as at Month 6 for all enrolled patients. Safety data will also be assessed at Month 6 for the first 30 patients enrolled as well as at Months 12 and 24, unless Year 2 treatment is delayed in which case the final safety assessment would occur at Month 30.

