To collect all serious adverse events (SAEs), adverse drug reactions (ADRs), adverse events of special interest (AESIs) and special situations during treatment with cladribine tablets over a 24-month period	SAEs, ADRs, AESIs	Adverse event (AE) collected from signed Informed Consent Form (ICF); Treatment- Emergent Adverse Events (TEAEs) considered after first treatment administration through the 24- month treatment period (or 30 months if Year 2 treatment is delayed)	Section 15
CCI			

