#### **15.1** Adverse Events

#### Definitions

The recording period for AEs begins when the patient is initially included in the study (date of signature of first informed consent) and continues at least to the end of the mandatory safety follow-up period (i.e., up to 24 months in most patients or up to 30 months in patients with delayed start of Year 2 treatment).

TEAEs: those AEs with onset dates occurring within the treatment period (that is after the first dose and until the end of the follow-up period).

For the analyses, ADRs will be those TEAEs reported in the eCRFs as related to study treatment or those AEs where such a relationship is missing.

All analyses described in Section 15.1 will be based on TEAEs if not otherwise specified.

Event rates (per patient-year of time on the study) will be calculated as the total number of events divided by the total time on study.

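### SAP 15 confines the safety analyses to the first 24 months, while SAP 5, SAP 15.1 and protocol 9.7 and 11.4 run safety to Month 30 when the Year 2 course is delayed

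*SAP*

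**What the plan says.** The opening sentence of SAP 15 sets the scope for the whole safety section: "Safety analyses will be done on the safety analysis populations, i.e. SAF for the first 24-month period".

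Other current text gives a longer period for patients with a delayed second course:

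- **SAP 5**, timeframe for the safety objective: treatment-emergent events count through the 24-month treatment period, "or 30 months if Year 2 treatment is delayed".
- **SAP 15.1**, recording period: "up to 24 months in most patients or up to 30 months in patients with delayed start of Year 2 treatment". Protocol 11.4 gives the same period.
- **SAP 15.1**, treatment-emergent events: those with onset "after the first dose and until the end of the follow-up period".
- **Protocol 9.7**: safety is assessed at Months 12 and 24, "unless Year 2 treatment is delayed in which case the final safety assessment would occur at Month 30".
- **Protocol 9.2.3**: follow-up lasts 24 months from first dose, or up to 30 months if low lymphocyte counts delay Year 2.

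For rates, SAP 15.1 says that they "will be calculated as the total number of events divided by the total time on study". Section 15 does not define time on study. The only definition in the SAP is in 14.1.1, for the annualized relapse rate: first dose to study completion or discontinuation, with no cap at Month 24.

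**The concern.** A programmer who takes the scope sentence of SAP 15 at face value stops at Month 24 for everyone. One who follows SAP 5 or the definitions in 15.1 continues to Month 30 for delayed patients. Both can cite current text.

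The patients affected are not a random subset. The protocol attributes a delayed second course mainly to lymphocyte counts that have not recovered (9.2.2, 9.2.3, 9.2.4). It also reports that herpes zoster was more frequent during Grade 3 or 4 lymphopenia (7.4). Months 24 to 30 in these patients are late follow-up after the second course, which is why the protocol extends observation for them. At stake is whether adverse events, deaths and laboratory values from those months reach the report, and whether event counts and patient-years cover the same time.

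**Working it through.** The plan states no figure to reproduce. The check compares the texts and then does simple person-time arithmetic.

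**1. Which text governs which output**

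| Place | Safety horizon | What it covers |
|---|---|---|
| SAP 15, scope sentence | first 24 months, no exception | all safety analyses |
| SAP 5 | 24 months, or 30 if Year 2 is delayed | treatment-emergent events |
| SAP 15.1 | end of follow-up (24, or up to 30) | analyses in section 15.1 |
| SAP 15.2 and 15.3 (deaths, SAE listing, laboratory) | none of their own | fall back on the SAP 15 scope sentence |
| Protocol 9.7 and 11.4 | 24, or 30 if Year 2 is delayed | safety assessment; AE recording |
| Protocol 8.2 and 9.1.2.3 | 24 months, no exception | safety objective and outcome |

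SAP 15.1 applies the treatment-emergent rule to the analyses described in that section. It does not reach 15.2 or 15.3, so it cannot settle the question for deaths, the SAE listing or laboratory data. The protocol is not uniform either.

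**2. Observation lost on the literal reading**

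SAP 6 moves the Year 2 visits out by at most 6 months. With the full delay, the second course starts at about Month 12 + 6 = 18 and follow-up ends at Month 30, which gives 12 months from that start. A cut at Month 24 keeps 24 − 18 = 6 of them and loses 6.

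**3. Rates if events stop at Month 24 but person-time does not**

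Let f be the share of patients delayed and d the delay in months. With a constant event rate and full follow-up:

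reported rate / true rate = 24 / (24 + f × d)

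The documents give no value for f, so 5% to 25% is assumed, with d = 6.

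| f | Calculation | Ratio | Too low by |
|---|---|---|---|
| 5% | 24 / 24.3 | 0.988 | 1.2% |
| 10% | 24 / 24.6 | 0.976 | 2.4% |
| 20% | 24 / 25.2 | 0.952 | 4.8% |
| 25% | 24 / 25.5 | 0.941 | 5.9% |

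Shorter delays do less: with d = 3 and f = 25%, 24 / 24.75 = 0.970.

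**4. Sensitivity to the constant rate**

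Suppose the monthly rate is 1 before the second course and k after it. Expected events are then 12 + 12k for an undelayed patient and 18 + 12k for a patient delayed 6 months, of which 18 + 6k fall before Month 24. With f = 25%:

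- k = 2: (0.75 × 36 + 0.25 × 30) / (0.75 × 36 + 0.25 × 42) = 34.5 / 37.5 = 0.920.
- k = 3: (0.75 × 48 + 0.25 × 36) / (0.75 × 48 + 0.25 × 54) = 45 / 49.5 = 0.909.

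With f = 5% the ratios are 35.7 / 36.3 = 0.983 and 47.4 / 48.3 = 0.981.

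**5. Consistent alternatives**

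If events and person-time both run to the end of follow-up, the ratio is 1.00. If both stop at Month 24, each rate is consistent within its window, but events in Months 24 to 30 are not reported.

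**The case against.** The strongest reply is that the sentence in SAP 15 names an analysis set and sets no event cutoff. The SAP's modification history shows that earlier versions had a separate safety-extension set, and that the latest version removed extension text from sections 15 and 15.1. The words about the first 24 months are probably a leftover contrast with that extension, and the 24-month label may be shorthand for the core study, delayed patients included. The more specific definition in 15.1 follows directly and keeps the late events. For laboratory data, SAP 9 assigns endpoints without an analysis window to the visit recorded in the eCRF, so a delayed final visit would still be tabulated.

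Most of this is fair as an account of what was probably intended. It does not remove the contradiction. The wording remains in current text, 15.2 and 15.3 have no time rule of their own, and the SAP 9 rule allocates visits without setting the safety period. SAP 6.5, which places the final analysis on the 24-month data, and the protocol's safety objective could both be cited for the shorter reading.

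The reply is also right about the rates. A rate is itself a safety analysis, so a Month 24 limit could apply equally to its numerator and denominator. The mismatch needs a mixed reading: section 15 binds the events, while the relapse-section definition of time on study supplies the denominator. That is possible, because no other definition exists, but it is not stated.

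**Conclusion.** SAP 15 is wrong as written: it contradicts SAP 5, SAP 15.1 and protocol 9.7 and 11.4 on when the safety period ends for patients with a delayed second course. The issue is minor. The main risk is that events, deaths and laboratory data from Months 24 to 30 are left out for patients who are mostly slow to recover their lymphocytes. The rate effect is secondary: about 1% to 6% too low, and only on the mixed reading, with a constant rate, a 6-month delay and an assumed 5% to 25% of patients delayed. It reaches about 9% if the rate is assumed to triple after the second course and 25% are delayed.

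Three stronger inferences are not supported:

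- **Loss of everything after a late second course.** Only what falls after Month 24 is at risk.
- **Diluted rates of special-interest events in delayed patients.** The arithmetic for one patient delayed 6 months is 24/30 = 0.80, but it matches no planned output. The visible SAP specifies patient-year rates for treatment-emergent events overall, for those leading to discontinuation or dose reduction, and for deaths. It plans none for herpes zoster, lymphopenia or infection, and none by delay status.
- **Events from the withdrawn 2-year extension left unreported.** Neither document says that any were collected or are in the database. The idea rests on change-log entries about superseded versions.

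**What to change.** In SAP 15, replace the phrase limiting the SAF to the first 24 months with: *SAF, from first dose to the end of follow-up (Month 24, or up to Month 30 if Year 2 treatment is delayed)*. Placed there, the rule covers 15.1, 15.2 and 15.3 alike.

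In SAP 15.1, add to the event-rate definition: *Event counts and patient-years use this same end date for each patient.*

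The cost is one reworded sentence and one added sentence, with the matching date rule in the programs. No new data collection or extra output is needed.
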